#### 6.2.1.3 Enrollment

Once a subject is deemed as eligible at screening they will be consented for enrollment into the study.

#### 6.2.1.4 Phase 1

The Day 0 evaluation should be scheduled within 45 days of the screening visit. Subjects will undergo training and instruction on the DHFS system and initiation of study drug with DOT. A clinical assessment including toxicity will take place on Day 0, Week 1, and Week 2. Subjects will be trained with the PDH system by study staff, including placing the patch under observation Day 0, Week 1, and Week 2. Subjects will begin DHFS IS-RM (or Rifamate with co-ingestion of an encapsulated edible sensor) on Day 0, which will be directly observed. Patients will have two study visits per week in Week 1 and Week 2 for directly observed ingestion of DHFS IS-RM (or Rifamate with co-ingestion of an encapsulated edible sensor). Monitoring for side effects will take place at visits. At the end of Week 2 the subject will have their plasma drawn and stored. All subjects will complete items on PDH system usability and satisfaction.

#### 6.2.1.5 Randomization

Subjects who wish to continue and remain eligible will be randomized 2:1 to DHFS IS-RM or to the control group receiving standard of care (SOC). Randomization for treatment assignment will be done centrally via the electronic database.

If the subject is randomized to the control arm, public health will provide isoniazid and rifampin, or Rifamate and DOT as per their routine. Please remind the subject to fill medication and contact public health as soon as possible. Please contact public health to inform them subject has been randomized to SOC DOT. The public health nurse assigned to this case should be handed the cost analysis data collection materials. The public health nurse will collect and perform quality control of the DOT forms used, but the outreach workers that actually perform the DOT.

If the subject is randomized to the intervention arm they will be given a 14-30-day supply of treatment medication, DHFS IS-RM, from the AVRC pharmacy on the entry day.

### 6.2.2 On-Study Evaluations, Phase 2

#### 6.2.2.1 Day 0

Subjects randomized to the intervention will undergo clinical assessment including toxicity. They will receive training and instruction will take place on home use of DHFS, continuous patch wearing, use of mobile device with application screen. They will be monitored for correct patch use. Pre-study interviews will collect subject attitudes to mobile devices

and internet usage, as well as their understanding of taking anti-mycobacterial medications thus far and what they would like to gain from use of the PDH monitoring system. Self-report questionnaires will be administered on a mobile device. The subject's plasma will be drawn and stored only if they are subjects seen at the AVRC. Cost data collected. The patient will be instructed to take IS-RM at the clinic. From this point on study personnel and public health workers will check adherence data provided by DHFS daily and perform adherence intervention as necessary.

#### 6.2.2.2 Week 2 to Completion of Treatment/End of Study

All subjects will receive a clinical assessment with toxicity and side effect evaluation, completion of a self-report adherence questionnaire and cost data collection. In the intervention arm, adherence will be checked (by reviewing DHFS logs) by study staff and public health daily and intervention will be performed as appropriate. At Weeks 2, 4, 8, and every 4 weeks until treatment is completed/end of study, adherence questionnaires will be collected; for subjects seen at the AVRC, Phase 2 visits will include a blood draw with stored plasma. In the intervention arm, the DHFS system usability and satisfaction questionnaires will be collected at Week 8, Week 12, and every 4 weeks until treatment is completed/end of study. For all subjects, at Week 8 and at the end of study, self-report questionnaires will be completed on a mobile device.

#### 6.2.3 Change in Anti-Mycobacterial Regimen

Intervention subjects who require a change their treatment regimen from DHFS IS-RM for any reason will be required to permanently discontinue their study regimens.

If the regimen change is due to microbiologic failure, the subject would be evaluated for microbiologic failure during physician clinic visits (Section 6.1).

#### 6.2.4 Post-Treatment Evaluations

All randomized subjects will complete an end of study visit, which will occur when a subject has completed their TB treatment (up to a maximum of 12 months on study). If the sponsor ends the study early, the end of study visit evaluation will be completed, regardless of week number.

#### 6.2.5 Premature Treatment Discontinuation

These evaluations are required at the subject's final visit if they stop the study any time before the end of their treatment.

#### 6.2.6 Pregnancy

Women who become pregnant during the study will be required to permanently discontinue their study regimens and will not continue to be followed on study. They should be advised to seek best available medical care for their pregnancy according to U.S. TB treatment guidelines.

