### 3.7 Discontinuation for Medication Related Toxicity

If the subject develops a toxicity that results in discontinuation of isoniazid and rifampin, or Rifamate, then an alternative medication regimen will be found and started as soon as feasible. The medication will not be supplied by the study. These patients will be required to permanently discontinue their study regimens but will continue to be followed for the duration of the study.

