#### 5.2 Regimens, Administration, and Duration

Study Treatment is defined as:

DHFS Group: over-encapsulated ingestion sensor plus a fixed-dose combination of isoniazid-rifampin (Rifamate) (study supplied) (alternatively in Phase 1, Rifamate with co-ingestion of an encapsulated edible sensor)

SOC Control Group: isoniazid plus rifampin, or Rifamate (by prescription)

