## 6.0 CLINICAL AND LABORATORY EVALUATIONS

### 6.1 Schedule of Events

Table 1.

Evaluation	Screening	Phase 1				Randomization	Phase 2							Completion of Treatment/ End of Study or Premature Discontinuation
		Week 1 Day 0	Week 1 Visit 1	Week 2 Visit 2	Week 2 Visit 3		Day 0	Daily	Weekly	Wk 2	Wk 4	Wk 8	Wk 12 and every 4 weeks	
Visit Window		Within 45 days of Screening								+ 7 days	+ 7 days	+ 14 days	+ 14 days	
Informed Consent	X													
Demographics and Language	X													
Documentation of TB	X													
Medical History	X													
Medication History (last 30 days)	X													
Toxicity/AE Evaluation	X	X	X	X	X		X			X	X	X	X	X
Targeted Exam	X	X					X			X	X	X	X	X
Concomitant Meds (since last visit)		X	X	X	X		X			X	X	X	X	X
Initiation of study medication		X					X*							
Randomization						X								
PDH System														
Subject training		X	X				X*							
Observation with PDH Patch		X	X	X	X		X*			X*	X*	X*	X*	X*
Patch change (by subject)		X		X			X*		X*					
Witnessed Rifamate doses		X	X	X	X		X*							
Adherence Intervention Based on PDH Sensor**								X*						

Evaluation	Screening	Phase 1				Randomization	Phase 2							Completion of Treatment/ End of Study or Premature Discontinuation
		Week 1 Day 0	Week 1 Visit 1	Week 2 Visit 2	Week 2 Visit 3		Day 0	Daily	Weekly	Wk 2	Wk 4	Wk 8	Wk 12 and every 4 weeks	
Laboratory Evaluations														
Hematology§	X						X			X	X	X	X	X
Liver Function Tests§	X						X			X	X	X	X	X
Chemistry§	X						X			X	X	X	X	X
Pregnancy Testing (and whenever pregnancy is suspected)	X	X												
Stored Plasma/Serum λ					X		X				X	X	X	X
Assessments														
Adherence Self-Report		X			X					X	X	X	X	X
Self-Report Questionnaires §§		X					X					X		X
Usability and Satisfaction Survey					X							X*	X*	X*

\* Subjects randomized to intervention arm only

\*\* Three visits for witnessed doses; phase1: Week 1 and Week 2

§ Done per standard of care within 30 days of screening and captured whenever done during the course of the study

§§ Habitual self-control, self-efficacy beliefs, depression scale (PHQ-9), alcohol use (AUDIT) and drug use (DAST-10) questionnaires

λ Only subjects seen at UCSD AVRC will undergo collection of plasma for storage.

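### Pregnancy ends on-study follow-up (6.2.6, 8.2) although a toxicity stop does not (3.7); no pregnancy outcome is collected, and 'study regimens' is unclear for the control arm

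*Combined protocol and SAP*

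**What the plan says.** Section 6.2.6 states that women who become pregnant "will be required to permanently discontinue their study regimens and will not continue to be followed on study". It continues: "They should be advised to seek best available medical care for their pregnancy according to U.S. TB treatment guidelines". Section 8.2 agrees, listing pregnancy among the criteria for discontinuation from the study.

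Section 3.7 treats a toxicity stop differently. Those patients also stop their study regimens permanently but "will continue to be followed for the duration of the study".

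On visits, 6.2.4 says: "All randomized subjects will complete an end of study visit, which will occur when a subject has completed their TB treatment". Section 6.2.5 covers early stoppers: "These evaluations are required at the subject's final visit if they stop the study any time before the end of their treatment". The Schedule of Events (6.1) puts both cases in one column, "Completion of Treatment/ End of Study or Premature Discontinuation".

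On safety, 6.4 keeps following serious adverse events that may be related to the device after a subject stops. Section 7.1 captures patch-related and sensor-related events to the end of exposure or to resolution. Section 6.3.9 provides pregnancy testing at screening, at entry and on suspicion, and no more.

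On the meaning of the regimen, 5.2 includes in its definition of study treatment "SOC Control Group: isoniazid plus rifampin, or Rifamate (by prescription", and 5.2.1 lists the same drugs as a regimen.

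**The concern.** Stopping a treatment and stopping observation are separate decisions. Section 6.2.6 joins them for pregnancy and 3.7 keeps them apart for toxicity, and no reason is given for the difference. Two kinds of information are lost.

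- **Safety.** Hypothesis 1.1.4 says the system is safe for use in TB treatment. Some pregnancies on study are foreseeable: women of childbearing potential may enrol if they agree to contraception (4.1.5), participation can last 12 months, and 5.5.3.1 lists hormonal contraceptives as precautionary with rifampin. The course and outcome of such a pregnancy have no place in the data collection described.
- **Randomised follow-up.** The Phase 2 endpoint (9.2.1) runs to end of study. A woman who leaves under 6.2.6 may still have TB treatment to finish, but her later adverse events, doses and treatment completion are not carried forward.

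There is also a wording problem. Section 6.2.6 is not limited to one arm, so on its literal words the instruction to stop reaches a control subject's own prescribed TB drugs.

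**Working it through.** **1. Two stopping rules compared**

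- Toxicity (3.7): regimen stops; follow-up continues to the end of the study.
- Pregnancy (6.2.6, 8.2): regimen stops; on-study follow-up stops.

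The instruction on the regimen is the same, and the instruction on follow-up is opposite.

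**2. What remains after a pregnancy stop**

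- Final-visit evaluations at the time of leaving: yes (6.2.5 and the shared column in 6.1).
- Serious events possibly related to the device: yes, until resolved or stabilised (6.4).
- Patch- and sensor-related events: yes, to end of exposure or resolution (7.1).
- Other adverse events after the final visit: no.
- Witnessed doses and TB treatment completion after the final visit: no.
- Pregnancy outcome: no provision in the supplied text. The serious-event definition in Table 2 does not name birth outcomes.

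County staff already collect witnessed ingestions, toxicity and hospitalisations in both arms as routine practice (3.5.1, 3.5.2), so most of what is lost has an existing source.

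**3. Expected number of pregnancies**

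The documents give no rates. Assumed: 20 to 30 women of childbearing potential, 0.5 year mean exposure, 2% to 10% pregnancies per year.

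Expected number = women × years × rate:

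- Low: 20 × 0.5 × 0.02 = 0.2
- High: 30 × 0.5 × 0.10 = 1.5

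**4. Effect on power**

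Inputs from 9.4: 50 and 25 subjects, 5-point difference, SD 6, two-sided alpha 0.05, stated power 92%. The noncentrality is 5 / (6 × √(1/50 + 1/25)) = 5 / 1.470 = 3.40 on 73 degrees of freedom. Power is 91.9% by the t-test and 92.5% by the normal approximation, so the plan's figure reproduces.

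Now suppose, more pessimistically than the plan implies, that a lost woman contributes no Phase 2 data at all:

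- 49 vs 25: 91.7%
- 50 vs 24: 91.2%
- 48 vs 24 (three women lost): 90.8%

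**5. Scoring of later doses**

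In the intervention arm the numerator in 9.2.1 counts only ingestions confirmed by the device; the denominator is prescribed witnessed doses. Once IS-RM stops, nothing can enter the numerator, and Section 9 does not say whether later prescribed doses stay in the denominator. To show the size, assume 95% before stopping (the planning value in 9.4), a stop after 25% to 75% of the prescribed doses, and all later doses counted as unwitnessed. One such woman then lowers the mean of 50 by 95 × (1 − f) / 50:

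- f = 0.75: 0.5 points
- f = 0.50: 0.95 points
- f = 0.25: 1.4 points

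If later doses leave the denominator, the shift is nil. The rule therefore needs stating, although few women would be affected.

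**6. 'Study regimens' by arm**

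- 5.2 and 5.2.1 place the control arm's prescribed drugs under study treatment and regimens.
- 5.4.1 says the study does not supply those drugs.
- 6.2.3 uses the same instruction to stop but limits it to intervention subjects.
- 6.2.6 has no such limit, yet its next sentence refers the woman to care under TB treatment guidelines.

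The literal scope and the apparent intent differ.

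**The case against.** The strongest reply is that a different rule for a different reason is a legitimate design choice, that 6.2.6 and 8.2 agree with each other, and that so few pregnancies could hardly inform hypothesis 1.1.4. The last part limits the importance of the point, but it does not explain why data that are cheap to keep should be given up.

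Four stronger readings are tempting, and the documents do not support them.

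- **That pregnant women are dropped from all follow-up.** Sections 6.2.5, 6.4 and 7.1 leave a final visit and continued follow-up of device-related events.
- **That 6.2.6 contradicts 6.2.4.** The words "All randomized subjects will complete an end of study visit" carry no exception, but 6.2.5, the shared schedule column and 8.2 provide an early-exit route. Otherwise every exit under 8.2, including a subject's own withdrawal, would contradict 6.2.4. It is a wording gap.
- **That these women leave the analysis set.** Section 9.6 includes every randomised participant dispensed at least one dose, and 9.6.1 says the mixed model accommodates subjects lost to follow-up. Her follow-up is cut short, but she stays in the set.
- **That the protocol intends to stop a control subject's TB drugs.** The County provides her treatment, the study does not supply it, and the sentence after the rule points to TB treatment guidelines. The intent is probably narrower. The ambiguity remains because 6.2.3 shows the authors limiting the same instruction to one arm.

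Nor can one say that pregnancy outcomes are never recorded: the consent pages were removed, and the manufacturer's reporting procedure cited in 7.1 is not available. Only the supplied text can be judged.

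**Conclusion.** The point holds as a cheap improvement in data collection plus a wording ambiguity to reconcile. Following 6.2.6 and 8.2 as written gives up safety information and later follow-up of a randomised subject, where 3.7 keeps follow-up after a comparable stop.

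The scale is small. The estimate of 0.2 to 1.5 pregnancies rests entirely on assumed inputs, and there may be none. The effect of the lost data on power is about 0.2 to 0.7 points for one woman (91.9 − 91.7; 91.9 − 91.2), which is negligible for the primary result. The unstated scoring of doses after IS-RM stops could matter more for an individual woman. Section 9.6 refers to a SAP for further detail, and the supplied text contains no rule on this.

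The scope of 'study regimens' in the control arm does not depend on these numbers. It concerns active TB treatment, and site staff should not have to infer the intent.

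**What to change.** 1. In 6.2.6 and 8.2, separate stopping the study regimen from stopping data collection. Continue passive follow-up from County records to the end-of-study point: adverse events and TB treatment completion in both arms, and witnessed doses in the control arm. A subject who withdraws consent stays free to leave.
2. Add one contact to record the pregnancy outcome.
3. In 9.2.1 or the SAP, state how doses prescribed after IS-RM stops enter the percentage for an intervention subject: counted as unwitnessed, removed from the denominator, or handled in another stated way.
4. Separately, the sponsor must reconcile what 'study regimens' covers in each arm across 5.2, 5.2.1, 5.4.1, 6.2.3 and 6.2.6. No clinical rule is proposed here.

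The cost is a few sentences of protocol text, consent wording for the continued record follow-up and outcome contact, and about one contact per pregnancy. Sample size and the planned model do not change.

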### 6.3 Special Instructions and Definitions of Evaluations

#### 6.3.1 Documentation of TB

The research coordinator will obtain results of any TB cultures, smears, cytology, and histopathology, from County records and medical records, and record them in the CRF.

#### 6.3.2 TB Drug Resistance Definition

Multi-drug-resistant tuberculosis (MDR-TB) is defined as tuberculosis that is resistant to at least isoniazid and rifampicin (RMP). Isolates that are multiply resistant to any other combination of anti-TB drugs but not to isoniazid and RMP are not classed as MDR-TB. Extensively drug-resistant tuberculosis is defined as TB that has developed resistance to at least rifampicin and isoniazid (resistance to these first line anti-TB drugs defines multi-drug-resistant tuberculosis, or MDR-TB), as well as to any member of the quinolone family and at least one of the following second-line anti-TB injectable drugs: kanamycin, capreomycin, or amikacin [22].

#### 6.3.3 TB Drug Resistance Testing

MDR-TB is defined by clinical, microbiologic, or molecular testing [23].

#### 6.3.4 Medical and Laboratory History

At screening, a medical history will be obtained and must be recorded in the source documents. The medical history should include detailed information on mycobacterial infection, clinical course, and drug susceptibilities.

#### 6.3.5 Medication History

At screening, a medication history (**only if within last 30 days prior to entry**) with actual or estimated start and stop dates should be obtained and recorded in the source documents and the concomitant medication CRF, including:

- All prescription medications. Including medications taken for the treatment or prophylaxis of opportunistic infections.
- Non-prescription medications.

- Alternative therapies and/or dietary supplements.
- Allergies to any medications and their formulations must be documented.

#### 6.3.6 Concomitant Medications

During study visits (see Section 6.1 for specific dates) all concomitant medications taken since the last visit will be recorded in the source documentation and entered into the concomitant medication log CRF.

#### 6.3.7 Study Treatment Modifications

All modifications to study drug(s) including initial doses, patient-initiated and/or protocol-mandated interruptions, modifications, and permanent discontinuation of anti-mycobacterials need be recorded on the CRFs at each visit.

#### 6.3.8 Clinical Assessments

##### Targeted Physical Exam

A targeted physical examination will be based on any signs or symptoms previously identified that the subject has experienced within 30 days of entry or since the last visit. This examination will be performed at Day 0 and at study visits, as specified in the Schedule of Events, and in instances of microbiologic failure/toxicity or premature treatment discontinuation if they should occur.

##### Height and Weight

Height and weight should be measured at study entry. Weight will be measured at every study visit.

##### Signs and Symptoms

All signs, symptoms, deaths, and toxicities must be documented in the subject's record. At entry, record all signs/symptoms experienced within 30 days of entry on the CRFs. For all other visits and at the time of occurrence of microbiologic failure, record all Grade  $\geq 2$  signs and symptoms and deaths on the CRFs that have occurred since the last visit. Any signs or symptoms that lead to a change in DHFS treatment or the investigator thinks could possibly be due to DHFS treatment, regardless of Grade, must be recorded on the CRF. The source document must include date of onset and date of resolution, but the CRF will only record prevalence of a given adverse event since the previous study visit.

Refer to the Division of AIDS Table for Grading Adult Adverse Experiences.

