## 7.0 CLINICAL MANAGEMENT ISSUES

### 7.1 Adverse Events

Adverse events will be captured by study personnel throughout a patient’s participation in both the active portion of the protocol as well as the follow-up period. Wearable sensor-related adverse events will be captured from the onset of exposure (e.g. first patch application) to the end of device exposure (e.g. removal of last patch, or resolution of last wearable sensor-related AE, whichever is later). Ingestible sensor-related adverse events will be captured from the onset of exposure (e.g. first ingestion) to the end of device exposure (e.g. last ingestion, or resolution of last ingestible-sensor related adverse event).

Table 2. Adverse Event-Related Definitions

Adverse Event (AE)	Any undesirable medical event occurring in research subject, whether or not the event is considered related to the investigational device.
Serious Adverse Event (SAE)	An AE that results in death, is life-threatening (even if temporary in nature), results in a permanent impairment of body function or permanent damage to body structure, hospitalization, prolongation of hospitalization, or medical or surgical intervention to preclude permanent impairment of a body function or permanent damage to a body structure, or represent a serious medical event. An SAE may or may not be considered related to the investigational device.
Anticipated Adverse Event (AAE)	An AE that is listed in the clinical protocol or other study-related document that has been identified as a potential AE related to the investigational device or procedure being studied.
Unanticipated Adverse Device Effect (UADE)	Any serious adverse effect on health or safety or any life-threatening problem or death caused by, or associated with, a device, if that effect, problem or death was not previously identified in nature, severity or degree of incidence in the investigational plan or application or any other unanticipated serious problem associated with a device that relates to the rights, safety or welfare of subjects.

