2. Skin changes that would be routinely encountered through the wear of a common adhesive bandage (e.g., transient wrinkling/whitening of the skin under a bandage, mild hyperemia).

Verification that a Skin Issue has Occurred

Before being classified as an AE, skin issues must be verified. Verification can consist of either: a) direct visualization by the investigator or his/her designee or b) a photograph taken of the affected area. The most convenient means to accomplish the latter will be use of the mobile device issued to each study subject; site staff should train each subject regarding the mobile device camera feature as he/she enters a given study. The only exception is pruritis that leads to interruption of system use > 1 day, as there likely will be nothing to visualize.

Documenting Skin AE Evolution and Chronicity

Skin AEs frequently last longer than 1 day, so a means to document the course of the AE is described below. Skin findings that occur in the same location should be treated as a single AE, unless complete resolution at that location has been visualized and documented by the investigator. Moreover, a skin AE may evolve over its course (e.g., erythema progressing to papules, followed by scaling). The investigator should therefore name the skin AE based upon findings first encountered (e.g., “macular rash”). For each assessment episode that occurs in follow-up, record the following on the *Adverse Events Form* case report form:

1. Date of assessment
2. Actions taken
3. Outcome, using the Table TBD
4. Any new features of the same skin AE that emerge on its course to resolution (e.g., scaling, non-erythematous skin discoloration) captured within the “additional skin findings” data field for a given skin AE
5. Date of onset and date of resolution

Table 4. Procedure for Documenting Device-Related Skin AE Outcome

Outcome	Definition	Action	CRF Used
Resolved	No remaining signs of skin changes	Document date of resolution	Adverse Event form used (for interim visits) OR Follow-up Visit form (for final study visit)
Resolving	Skin changes have improved but are still discernible	Document as “resolving” List any new skin findings Must continue surveillance through last study visit	Adverse Event form used (for interim visits) OR Follow-up Visit form (for final study visit)

Outcome	Definition	Action	CRF Used

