### 9.6.2 Analysis for Secondary Outcomes

All secondary measures will be summarized descriptively by study arm and overall. Mixed effects regression models analogous to the primary analysis methodology will be applied for the secondary outcomes. There will be no adjustments made for multiple testing corrections for secondary outcomes. P-values less than 0.05 will be considered statistically significant.

The percentage of subjects completing > 80% prescribed witnessed dosing for TB treatment using DHFS and SOC, respectively will be calculated and compared using two sample t-tests (or non-parametric equivalent) for the duration of follow-up. The time to first evidence of < 80% adherence will be calculated in the DHFS only as this may not be available in the SOC data.

The number of lapses in witness doses will be compared between DHFS and SOC using Wilcoxon rank sum test. The longest duration of lapse in witnessed treatment will be calculated and compared between the DHFS and SOC groups.

Data collected and model considerations for the costs analyses will include: 1) number of visits from outreach worker divided by length of time on study, 2) outreach worker hours spent per subject divided by length time on study; 3) distanced traveled per subject divided by length of time on study; 4) distance traveled by outreach worker divided by length of time on study, and 6) number of hospitalizations divided by length of time on study. Patient travel costs and lost wages will be reported. Wage costs with benefits of County workers and time spent per case will be calculated. Sensitivity analyses as appropriate with variation of costs and rates of failure derived from pre-existing County data will be performed of DHFS and DOT and will include all costs related to TB treatment, laboratory monitoring, assessment and treatment of adverse events, costs of DHFS and equipment associated with DHFS.

Adverse events related to study procedures (either DHFS or SOC DOT) will be graded using standard ACTG grading tables and listed by organ system and severity. Of note, GI symptoms, hepatic enzyme abnormalities, or other expected toxicities of Rifamate or TB disease itself that were pre-existing and were not exacerbated during the study will be recorded, but will not be adjudicated as related or possibly related to DHFS.

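### For non-skin symptoms the CRF holds prevalence per visit interval but no dates, so ongoing and recurrent events, and those spanning the start of Phase 2, cannot be told apart in the database

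*Combined protocol and SAP*

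**What the plan says.** Section 6.3.8 (Signs and Symptoms) sets the general rule. The source document must carry onset and resolution dates, but "the CRF will only record prevalence of a given adverse event since the previous study visit". After entry, the CRF takes signs and symptoms of Grade 2 or higher. Lower grades are added only if they change DHFS treatment or the investigator thinks DHFS could be the cause. At entry, all symptoms from the preceding 30 days are recorded.

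Section 7.2 sets a different rule for skin events: "For each assessment episode that occurs in follow-up, record the following on the" Adverse Events Form, and the list that follows includes "Date of onset and date of resolution". It also says when a finding is new: "Skin findings that occur in the same location should be treated as a single AE", unless complete resolution there has been documented.

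Two other parts of the plan turn on timing. Section 7.1 sets the capture window by exposure: "Ingestible sensor-related adverse events will be captured from the onset of exposure (e.g. first ingestion) to the end of device exposure". Section 9.6.2 treats separately the expected toxicities of Rifamate or of TB "that were pre-existing and were not exacerbated during the study will be recorded"; these are not judged related to DHFS. Section 9.6.2 also has all secondary measures summarised by arm and overall, and adverse events are secondary objective 1.2.6.

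**The concern.** A prevalence record answers one question: was the symptom present at any time since the last visit? It does not say whether the symptom is the same episode as before, when it began or when it ended.

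The design makes this more than a formality. Under Sections 3.0 and 3.5, all subjects take the ingestible sensor and wear the patch in Phase 1, including those later randomised to standard-of-care DOT. A control's symptom soon after randomisation may be left over from sensor exposure or may be new under DOT. A by-arm summary needs a rule for such cases, and the rule needs an onset date. Hypothesis 1.1.4 (DHFS is safe) and objective 1.2.6 draw on these records, and Section 9.5 relies on monthly review by the study team without an independent board.

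**Working it through.** The plan states no figure on this point, so the check is to set the rules side by side and ask what each pattern of records can identify.

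Inputs:
- Section 6.1, Table 1: the row "Toxicity/AE Evaluation" is marked at screening, all four Phase 1 visits, Phase 2 Day 0, Weeks 2, 4 and 8, Week 12 and every 4 weeks, and end of study. It has no intervention-only asterisk.
- Section 11.1.3: eCRFs are tied to scheduled visits, so each prevalence record covers a known interval.
- Section 6.3.9: blood counts, creatinine, liver enzymes and bilirubin go on the laboratory CRF at every value, whatever the grade.
- Sections 6.3.8, 7.2 and 9.6.2 as described above.

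Patterns for a non-skin symptom:
1. Marked in Phase 1 or at Phase 2 Day 0, and not afterwards. The Day 0 record looks back over time before Phase 2, so the event belongs to Phase 1. Resolved.
2. Not marked up to and including Day 0, first marked at Week 2 or later, with no milder form before. The event belongs to Phase 2. Resolved to within a visit interval.
3. Marked at two consecutive visits. One continuous event and two separate events give the same records. Not resolved.
4. Marked in Phase 1 or at Day 0, and again at Week 2. Carry-over and recurrence give the same records. In a control, the first began under DHFS and the second under DOT. Not resolved.
5. Grade 1 in Phase 1 and not suspected to be due to DHFS, then Grade 2 at Week 2. The Phase 1 episode need not be on the CRF, so the event looks new when it is a worsening. Not resolved.
6. A control without a Day 0 toxicity assessment. Table 1 schedules one for everyone, but Section 6.2.2.1 describes it only for the intervention arm. If a site follows the latter, the Week 2 record reaches back to the last Phase 1 visit and mixes both exposures. Not resolved.

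Skin events do not meet these problems, because both dates are on the CRF. Laboratory toxicities can be followed through serial values.

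Scale: the documents give no rate for symptoms that span Day 0. As an illustration only, assume that the nausea and vomiting rates they cite apply to Phase 1: 1% from the device label (Section 2.2) and 3.5% for an earlier prototype (Section 7.2).
- 25 controls: 25 × 0.01 = 0.25 and 25 × 0.035 = 0.9 expected subjects.
- 75 randomised subjects: 75 × 0.01 = 0.75 and 75 × 0.035 = 2.6 expected subjects.

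Only some of these would persist or recur across Day 0. Symptoms due to the TB drugs or the disease would add to them, but the documents give no rate for those.

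**The case against.** The strongest reply is that most of the information survives. Records are linked to visits, adverse events are evaluated at Day 0, and first occurrences can usually be placed in a phase. Skin events, which made up 61 of the 62 patch-related adverse events in the device label, are fully dated. Section 7.1 asks the investigator to weigh onset and duration when judging cause, and the investigator has the source document. Symptoms before entry are on the CRF. The planned analysis is descriptive, in a pilot study. All of this stands, and it narrows the point to patterns 3 to 6.

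Several stronger readings are tempting but not supported:
- A reader might infer that the database cannot separate Phase 1 from Phase 2 events at all. Patterns 1 and 2 show otherwise.
- A reader might infer that device effects are hidden in the control arm. Section 9.2.2 defines the endpoint by relationship to DHFS or DOT, so a sensor-related event in a future control can still be attributed to DHFS.
- A reader might infer that long events are multiply counted. One persistent event could produce 3 records in a subject with the 4-week minimum (Day 0, Week 2, Week 4/end). It could produce 4 + 10 + 1 = 15 in a subject followed past Week 48 (Day 0 and Weeks 2, 4 and 8; Weeks 12 to 48; end of study). But the plan nowhere says that records will be counted as events, and subjects with at least one event can be recovered from prevalence records.

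What the reply does not remove is that the judgement of pre-existing or exacerbated, and any by-arm summary of non-skin symptoms, cannot be checked from the database in those patterns. The dates could be retrieved from source, but the plan does not provide for it.

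**Conclusion.** The point holds for signs and symptoms outside the skin rule. Sections 6.3.8 and 7.2 differ on whether adverse event dates belong on the CRF. Under the general rule the database cannot separate ongoing from recurrent non-skin symptoms. It also cannot resolve those recorded on both sides of Phase 2 Day 0, or those below the CRF threshold in Phase 1 and worse later. Skin events, laboratory values and first occurrences clearly within one phase are not affected.

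The number of events concerned is probably small for sensor-related symptoms and unknown for drug-related ones. No bias in the safety comparison has been shown. This is a worthwhile, inexpensive improvement to the safety data rather than a flaw that threatens the trial's conclusions. It rests on the protocol text: the eCRF itself is not in the documents and may hold more than Section 6.3.8 says. Section 9.6 leaves detail to an SAP to be finalised before database lock. That SAP could supply an attribution rule, but not dates that were never entered.

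**What to change.** 1. In Section 6.3.8, replace the prevalence-only rule so that it agrees with Section 7.2. For every recorded adverse event the CRF carries onset date and resolution date (or ongoing), copied from the source document.
2. In Section 9.6.2 and the SAP, assign each adverse event to the phase and monitoring method in use at onset. Report the number of distinct events and the number of subjects with at least one event. Person-time rates are optional.
3. Reconcile Table 1 with Section 6.2.2.1 on whether controls have a toxicity assessment at Phase 2 Day 0.

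The cost is two date fields on the adverse event form, a sentence in each of two sections, and a small amount of data entry. Because the protocol describes a study already under way (the PK substudy ended in November 2014), events already entered would need their dates filled in from the source documents, which Section 6.3.8 already requires to hold them.
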